October
2025

Women Supporting Women Using Local Solutions to Improve Infant and Young Child Feeding and Care Practices in Punjab, Pakistan

STUDY PROTOCOL

Study Overview

JUSTIFICATION.

This study responds to a call by the Pakistani government and public health researchers who have identified combatting child malnutrition as a high priority for Rahim Yar Khan (RYK) district in the province of Punjab. This study will focus on the proximal causes of malnutrition (inadequate diet and infections).

GOAL.

To rehabilitate moderately malnourished children 7-23 months of age and enable mothers to sustain this healthy growth at home by changing their infant and young child feeding (IYCF), care, hygiene, and health-seeking behaviors.

PURPOSE.

The OVERALL STUDY PURPOSE is to develop and evaluate a behavior change educational program to prevent malnutrition in the province of Punjab, Pakistan. The study has two main phases: the Formative Research Phase and the Intervention Phase.

The PURPOSE OF THE FORMATIVE RESEARCH is to identify uncommon but successful (i.e. *Positive Deviant*) IYCF behaviors practiced by local mothers of well-nourished children from economically disadvantaged homes, and to develop an education program informed by these best-practices and WHO guidelines.

The PURPOSE OF THE INTERVENTION PHASE is to deliver the educational program to mothers with undernourished children in the Intervention arm of the study who are equally disadvantaged, and to evaluate its impact on the growth of children.

STUDY HYPOTHESIS.

The primary hypothesis is that a higher proportion of Index children in the intervention compared to the control group will experience an average weight gain of 400g/month in the first 4 mos of the intervention.

STUDY OBJECTIVES.

1. Understand local perceptions, experiences, and cultural norms around IYCF practices and care,
2. Discover demonstrably successful IYCF behaviours and strategies using local resources,
3. Develop and implement a culturally appropriate and context-specific intervention,
4. Evaluate the intervention using two comparisons: (a) Within the intervention group: assess Index children's growth patterns and change in household behaviours/factors relevant to IYCF (e.g., knowledge, practice, beliefs and norms). (b) Intervention vs control group: compare average weight gain of Index children and household behaviours/factors relevant to IYCF (e.g., knowledge, practice, beliefs and norms)

Research Methods

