To reinforce the intervention, supplemental printed materials will be distributed to households during the 28-day program. These materials will be developed in collaboration with the CAC and based on findings from formative research. Designed to be accessible to illiterate populations, the materials will feature culturally relevant visuals with minimal text and be tailored for both men and women. An estimated 5,000 copies will be produced for dissemination to those participating in the 28-day behavior change program as well as the sensitization program.

EVALUATION

The project will evaluate the intervention’s effectiveness, study Objective #4. Evaluation tools have been adapted from existing validated instruments, informed by the formative research phase, reviewed by the CAC for clarity and cultural appropriateness and pilot tested. All tools have been translated to the local Punjabi dialect spoken by both Punjabi and Saraiki tribes residing in Rahim Yar Khan. Both the Treatment and Control Arm households will undergo the similar evaluations.

The evaluation will involve two major data collection strategies.

BASELINE AND FOLLOW-UP SURVEYS

Interview-assisted surveys will be conducted with mothers. These surveys will gather information on demographics, child health status, infant and young child feeding (IYCF) practices, hygiene behaviours, healthcare-seeking behaviours, gender norms, psychosocial factors, and available resources. Baseline surveys will be conducted after households have

consented to participate. Follow-up (Endline) survey will be conducted 6-months after the baseline surveys. With the exception of demographic information, which will only be obtained once at baseline, both baseline and endline surveys will obtain the same information. A third survey will be conducted 12 months post-intervention, if funding permits.

ANTHROPOMETRIC MEASUREMENTS (Weight and Height).

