Anthropometric data will be collected by trained study staff to measure children's height and weight. Measurements will be taken with calibrated tools to minimize observer bias, and analyzed using WHO Anthro software to determine nutritional status based on standard Z-scores (weight-for-age, height-for-age, and weight-for-height). Children will be classified as underweight, stunted, wasted, or well-nourished. For the Treatment and Control Arm children, anthropometric measurements will be obtained at the time of recruitment, part of the baseline survey, during monthly follow-up, and part of the endline survey. Additionally, for the children in the Treatment Arm, weight will be collected during the 28-day behavior change practice program (Days 1, 13, and 28).

Inclusion Criteria

INTERVENTION PHASE

Eligible participants must meet all of the following conditions:

Child-Level Criteria:

- While children in the intervention phase will range from ages 7-23 months, At the time of recruitment children will range from Ages: 7–15 months.
 - Priority will be given to younger children, aged 7–11 months followed up by 12–15 months, to allow completion of the intervention and follow-up visits before the child turns 24 months of age, as complementary feeding refers to feeding practices between the ages of 6–24 months.
 - Moderate malnutrition, defined by: Weight-for-age Z-score between -2 and -3 standard deviations.

Household-Level Criteria:

- Households will be eligible to participate if:
 - They meet the classification of very poor or poor (based on community-defined wealth stratification).
 - Have access to clean water and sanitation.
 - Food secure at time of recruitment, defined as:
 - On government assistant program or at least one adult has permanent employment, or two or more have temporary employment.

- Ownership of at least one simple livestock (e.g., chicken, goat, or sheep).
- Access to a kitchen garden, or willingness to establish one with study support

Mother Eligibility Criteria:

The household is eligible only if the mother meets all of the following:

1. Mother is the primary caregiver for the Index Child (responsible for daily care, including supervision, bathing, and feeding).
2. Mother is alive and at least 18 years old.
3. Mother is currently breastfeeding the Index Child and willing to continue until the child reaches 2 years of age.
4. Mother expresses an interest in participating in the PD/Hearth program.

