Anthropometric Assessment. Each Index Child's weight and height will be measured at the start and end of each hearth session, and at the end of the 2-week home visits (Day 1, Day 13, Day 27 of each cycle). If, by the end of the cycle, the child has not gained at least 400g, they will be invited to repeat the cycle—up to a maximum of three cycles. Children failing to any gain weight between cycles will be referred to a public health facility for medical evaluation. Z-Scores will be calculated to quantify the child's nutritional status. Mid-Upper Arm Circumference (MUAC) will be taken to assess for wasting. During the follow-up period, the child's weight will be monitored monthly for up to six months post-intervention.

Health assessment.

Baseline health assessments will be conducted at local public health facilities within two weeks prior to the first Hearth session for participants in the treatment arm. Each Index Child will receive a full medical examination by a physician, a Hematocrit (Hb) test via finger prick, and verification and updates for routine immunizations.

All children showing "failure to thrive" (e.g., no weight gain or weight loss after a Hearth cycle) will be referred for medical assessment within five days, and accompanied by study staff.

Results of participants' health assessments will not be shared or retained by the research team. This assessment will be conducted solely to confirm that the child meets eligibility criteria and is well enough to participate in the 28-day behaviour change program. This information is sufficient for enrollment purposes, and no medical or health records beyond the anthropometric measurements will be collected, stored, or used as study data

Data collection

Data will be collected using structured tools and include:

Baseline and follow-up household surveys (at 6 months, and possibly 12 months post-intervention if funding permits): surveys will assess 24-hour food recall and indicators on feeding practices, WASH, gender roles, and health-seeking behaviour. Study survey instrument is attached to Section 9.5.

All data will first be recorded on paper and later digitized by trained personnel.

PROCEDURES FOR PARTICIPANTS IN THE CONTROL ARM

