Participants in the control group will be enrolled after staff use the Final Recruitment Screening for Control Form to confirm eligibility, and households that express interest will be invited to join. Unlike the intervention group, control participants will not undergo a health facility-based assessment at baseline, will also not participate in the 28-day behavior change practice program, and will instead continue to receive routine care from LHWs and access health services as usual.

They will participate in the baseline and follow-up household surveys (at 6 months, and possibly 12 months post-intervention if funding permits): surveys will assess 24-hour food recall and indicators on feeding practices, WASH, gender roles, and health-seeking behaviour. Study survey instrument is attached to Section 9.5.

Anthropometric Assessment. Each Index Child's weight and height will be measured at the time of baseline and endline survey. Z-Scores will be calculated to quantify the child's nutritional status. Mid-Upper Arm Circumference (MUAC) will be taken to assess for wasting. During the follow-up period, the child's weight will be monitored monthly for up to six months post-baseline.

Time to Participate

For Treatment arm:

If a household were to partake in one hearth cycle and complete the full 6-month participation we will be offering, we can estimate the total time participants would need to commit is 40 hours over a 6-month period.

- initial recruitment assessment 0.5 hours,
- consent signing 0.5 hours,
- baseline survey 1.25 hours,
- final 6-month survey 1 hour,
- anthropometric measurement 1.5 hours (0.25 hours x 6, includes measurement taken at baseline, follow-up, and final assessment).
- 28-Day Behavior Change Practice Program. Hearth Sessions Total 34.5 hours: 12 days per cycle, 2.5 hours per day, for total = 30 hrs. Home-visits during the second half of the program total of 4.5 hours (1.5 hours three time a week for two weeks),
- Health Assessment at the medical facility may take up to 1 hour for medical screening, immunization checks, and collection of baseline height and weight measurements.

If the household participates in three hearth cycles, the time the staff will spend at the family's home is estimated to be 74.5 hours.

For Control arm:

If a household were to complete the full 6-month participation, we can estimate the total time participants would need to commit is 4.75 hours.

- initial recruitment assessment 0.5 hours,

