- consent signing 0.5 hours,
- baseline survey 1.25 hours,
- final 6-month survey 1 hour,

- anthropometric measurement 1.5 hours (0.25 hours x 6, includes measurement taken at baseline, follow-up, and final assessment).

Obtaining Consent

On the day of final recruitment, details of the study and the consent process will be explained to mothers. Households will then have one week to reflect on the information provided. During a home visit one week later, and just before the baseline survey, trained staff will obtain informed consent from the mother of the index child. The staff has gone through training to ensure they communicate the following in lay-person language, and in a clear and respectful manner: research time-frame; title of research; researchers involved; purpose of research; description of research; potential harms and benefits; treatment alternatives; statement of confidentiality; information and data to be collected; how long the data will be kept, how it will be stored and who can access it; any conflicts of interest; a statement of the participant's right to withdraw from participation at any point; and a declarative statement of understanding that the potential participant agrees to and signs.

- A copy of the consent form will be provided to the parents of Index child.
- Parents will authorize by signing the consent form that they have read and understand this consent form, and volunteer to participate in this research study.
- For eligible participants with limited literacy, parents will authorize using thumbprint signature that they understand the consent form and volunteer to participate in this research study.

Informed Consent from the Treatment Arm households will be obtained 1 week after communicating the study information with the participants, and 1-2 weeks prior to the 28-Day Behavior Change Practice sessions, and before participants participate in the baseline survey.

Informed Consent from the Control Arm households will be obtained 1 week after communicating the study information with the participant, and before participants in the baseline survey.

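### Weight monitoring is timed from different events in the two arms, and the 4-month primary window has no starting event in controls, so no common month-4 weight is fixed

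*Protocol*

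**What the plan says.** The Study Hypothesis in the Protocol is that more intervention than control children will "experience an average weight gain of 400g/month in the first 4 mos of the intervention". Controls do not take part in the 28-day program (Procedures for Participants in the Control Arm), and no section gives them a substitute start date.

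The two parallel paragraphs on anthropometric assessment differ. In the treatment arm weight is "monitored monthly for up to six months post-intervention"; in the control arm it is "monitored monthly for up to six months post-baseline". The 28-Day Behavior Change Practice Program Overview agrees with the treatment-arm paragraph: monthly check-ins begin once a cycle ends with the growth milestone met, and then run for up to 6 months.

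Other places describe one clock. The Summary of the intervention gives 6 months of follow-up and support. Baseline and Follow-up Surveys says "Follow-up (Endline) survey will be conducted 6-months after the baseline surveys", with no distinction by arm. The Evaluation section says that for both arms "anthropometric measurements will be obtained at the time of recruitment, part of the baseline survey, during monthly follow-up, and part of the endline survey".

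Under Obtaining Consent, treatment-arm consent is taken just before the baseline survey and "1-2 weeks prior to the 28-Day Behavior Change Practice sessions". The child-level inclusion criteria give priority to younger children "to allow completion of the intervention and follow-up visits before the child turns 24 months of age".

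**The concern.** The primary endpoint is a threshold on average monthly gain. A comparison of the share of children above a threshold is fair only if gain is measured over the same length of time in both arms, or is properly scaled for time. Here the window is named by an event that only one arm experiences. In the treatment arm it could start at either of two weighings, and the monthly visits that should supply the month-4 weight are tied to different events by arm.

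At stake is whether a usable month-4 weight exists on the same schedule in both arms. If the monthly visits of treated children are counted from the end of their last cycle, their timing also depends on response, because children who have not gained 400 g repeat cycles. A later definition of the endpoint can rescale for time, but it cannot supply a weight that was not taken near month 4. The same wording also strains the stated reason for favouring younger recruits.

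**Working it through.** **Inputs from the Protocol.** Lag from baseline survey to first Hearth day: 7-14 days (Obtaining Consent). Cycle length: 28 days, one to three cycles, so 28-84 days. Threshold: 400 g/month over 4 months, which is 1,600 g if a nominal 4 is the divisor. Convention: 1 month = 30.44 days. The protocol states no growth mean or SD; those in step 4 are assumptions. The sample-size figure plays no part.

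**1. End of monitoring, read literally.** Controls: 6.00 months after baseline. Treatment: (lag + cycles)/30.44 + 6.
- One cycle, 7-day lag: (7 + 28)/30.44 + 6 = 7.15 months.
- Three cycles, 14-day lag: (14 + 84)/30.44 + 6 = 9.22 months.

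Neither agrees with a 6-month total from baseline.

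**2. Treated check-in nearest month 4, if monthly visits count from the end of the last cycle.** Months after baseline:
- One cycle: (35 to 42)/30.44 + 3 = 4.15 to 4.38.
- Two cycles: (63 to 70)/30.44 + 2 = 4.07 to 4.30.
- Three cycles: (91 to 98)/30.44 + 1 = 3.99 to 4.22.

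The control visit is at 4.00. The treated visit moves with the number of cycles.

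**3. Length of the primary window under each possible rule.** The lag is 7/30.44 = 0.23 to 14/30.44 = 0.46 month.
- A. Both arms from baseline to baseline + 4, or treated from Hearth Day 1 to Day 1 + 4: 4.00 against 4.00.
- B. Treated from the baseline weight to Hearth Day 1 + 4: 4.23 to 4.46 against 4.00. With a nominal divisor of 4, the treated rate is inflated by 5.7% to 11.5%, and a true rate of 1600/4.23 = 378 down to 1600/4.46 = 359 g/month passes as 400.
- C. Treated from the Hearth Day 1 weight to baseline + 4: 3.77 to 3.54 against 4.00. With a divisor of 4, a true 1600/3.77 = 424 up to 1600/3.54 = 452 g/month is needed to reach 400.

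If gain is divided by actual elapsed time, the difference in window length drops out of the rate under every rule.

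**4. Illustration of the responder rate with no treatment effect.** Monthly gain is assumed normal with SD 100 g/month. The control rate is 1 - Φ((400 - mean)/SD); for treated children 400 is replaced by the passing rate from step 3.
- Mean 300: control 15.9%; rule B 21.7% to 27.8%; rule C 10.7% to 6.4%.
- Mean 200: control 2.3%; rule B 3.7% to 5.6%; rule C 1.2% to 0.6%.

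The artefact can run either way, and its size depends heavily on the assumed mean.

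**5. Age at the last treated weight, read literally.** Consent comes one week after recruitment, so with three cycles the last weight falls (14 to 21 + 84)/30.44 + 6 = 9.22 to 9.45 months after recruitment.
- Recruited at exactly 15.0 months: 24.2 to 24.4 months.
- Age at recruitment above which 24 months is passed: 24 - 9.45 = 14.55 to 24 - 9.22 = 14.78 months.
- If the upper limit means 15 completed months (15.99): 25.2 to 25.4 months.
- One cycle, even from 15.99: 15.99 + (42 to 49)/30.44 + 6 = 23.4 to 23.6 months, so no breach.
- Two cycles, (70 to 77)/30.44 + 6 = 8.30 to 8.53 months: 23.3 to 23.5 from 15.0, but 24.3 to 24.5 from 15.99.

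**The case against.** The best defence is that this is loose wording, not two designed clocks. The endline is six months from baseline in both arms, the anthropometry schedule is listed jointly, the time budgets allow six measurements per child in each arm, and treated participation is put at six months. The protocol even dates a possible control-arm survey from the end of the intervention, so the term is not used strictly. Up to six months is a ceiling. The endpoint is phrased as a monthly average, and a statistical analysis plan would normally name the baseline record, visit window and divisor.

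Much of this stands. A reader might infer that the protocol starts the 4-month clock at different events in the two arms and so credits treated children with extra growth. It does not say so: it gives controls no start at all. Rule B needs a baseline start, an end four months after Hearth Day 1 and a nominal divisor, none of which is stated, and rule C reverses the direction. Treated weights after month 6 have a legitimate within-arm use, and no stated between-arm comparison relies on them. The age breach needs late recruitment, repeat cycles and the literal treatment-arm wording.

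It does not dispose of the point. The two monitoring paragraphs govern when children are weighed, and they disagree with each other. An analysis plan can define a divisor, but it cannot restore a month-4 weight that was not collected.

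**Conclusion.** The point holds as a contradiction in the monitoring schedule combined with an undefined origin for the primary window. It is not a demonstrated bias in favour of treatment.

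The possible mismatch in growth time is 0.23 to 0.46 month on a 4-month window. It arises only with raw gains over unequal windows or a nominal divisor, and its direction depends on the origin chosen. The responder-rate figures illustrate sensitivity under assumed growth; they are not estimates for this trial. The 6-month endline comparison has a common clock and is sound on this point.

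The literal end of treated weighing, 7.2 to 9.2 months after baseline, cannot be squared with the 6-month total. It would take recruits older than about 14.6 to 14.8 months past 24 months if they need three cycles. The correction should be made before recruitment, because it protects the primary comparison at almost no cost.

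**What to change.** - In the Study Hypothesis, define month 0 in both arms as the baseline-survey weighing. Define the endpoint as (month-4 weight minus baseline weight) divided by actual elapsed days, multiplied by 30.44, and compared with 400 g/month.
- In both anthropometric assessment paragraphs, schedule a month-4 weighing counted from baseline, with the same visit window in each arm, whichever cycle a treated child is in.
- Restrict between-arm comparisons to visits on this common clock. Treat the extra Hearth weighings and any treated weights after month 6 as within-arm description.
- Reconcile the follow-up duration in the 28-day program overview and the treatment-arm assessment paragraph with the Summary, the survey schedule, the joint anthropometry schedule and the control-arm paragraph. Labelling later treated weights descriptive does not by itself keep the oldest recruits under 24 months, so the age rationale must be checked against whichever duration is kept.

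The cost is mainly wording. Monthly weights are already planned in both arms; at most, some treated children's month-4 visit moves by a few days or weeks.

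### Control children are weighed monthly by study staff, but no study referral rule covers stalled or falling weight until they become severely malnourished

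*Protocol*

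**What the plan says.** The protocol has four kinds of referral rule.

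- **Both arms.** The Summary under Implementation of the Intervention sends severely malnourished children to local facilities whichever group they are in. Recruitment Methods, item 4 (Eligibility Assessment), repeats this at screening.
- **Treatment arm, programme overview.** The 28-Day Behavior Change Practice Program Overview refers non-responders to the cycles for medical evaluation.
- **Treatment arm, Anthropometric Assessment.** "Children failing to any gain weight between cycles will be referred to a public health facility for medical evaluation".
- **Treatment arm, Health assessment.** Children showing failure to thrive are referred, with the example "no weight gain or weight loss after a Hearth cycle) will be referred for medical assessment within five days, and accompanied by study staff".

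Monthly weighing runs in both arms. Under Anthropometric Measurements, for treatment and control children alike, "anthropometric measurements will be obtained at the time of recruitment, part of the baseline survey, during monthly follow-up, and part of the endline survey". The treatment-arm procedures add that "weight will be monitored monthly for up to six months post-intervention"; the control-arm procedures say that "weight will be monitored monthly for up to six months post-baseline".

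On care for the control arm, the protocol says that "control participants will not undergo a health facility-based assessment at baseline" and that these children "continue to receive routine care from LHWs and access health services as usual". Both arms enter on the same criterion: "Weight-for-age Z-score between -2 and -3 standard deviations".

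**The concern.** The sponsor has already decided that a moderately underweight child who gains nothing over one 28-day cycle should see a clinician within five days. Study staff will hold much the same signal, a weight about every four weeks, for children in the control arm. The control-arm procedures do not say what staff should do when that weight is flat or falling.

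What is at stake is child safety. Control children start in the same weight-for-age band and are examined less at entry. Chronic illness is ruled out from the mother's account and Lady Health Worker records, whereas treated children also need facility clearance, which item 5 (Consent Process) describes as a second check. An illness behind poor growth is thus more likely to pass unnoticed into the arm where the written safeguard is weaker.

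**Working it through.** **Step 1: set the rules side by side.** The protocol states no figure to reproduce, so this is a reading of the text.

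| Children | Study trigger at severe malnutrition | Study trigger short of severe malnutrition |
|---|---|---|
| Treated, in cycles | Yes | Three: non-response, no gain between cycles, failure to thrive |
| Treated, graduated to monthly check-ins | Yes | None explicit; the failure-to-thrive wording can be read to cover them |
| Control | Yes | None |

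All three rules in the last column depend on Hearth cycles or stand under the treatment-arm heading. Control children attend no cycle.

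**Step 2: illustrate what waiting for the severe trigger could mean.** A child whose weight stays flat loses weight-for-age Z as age advances, so persistent faltering does move the child toward the severe trigger. The question is how late that trigger comes.

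Inputs:
- Entry value z0: -2.25, -2.5 or -2.75, all inside the -2 to -3 band in the Inclusion Criteria.
- Loss rate d under flat weight: 0.1, 0.2 or 0.3 Z per month. **This is an assumption; the protocol gives no rate.**
- Severe taken as weight-for-age below -3. **This is also an assumption:** the Summary does not define the term.
- Follow-up: 6 monthly weighings.

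Formula: Z at month m is z0 - d × m. The severe trigger fires at the first whole m with z0 - d × m < -3. The treatment-arm rule, if extended, fires at m = 1. The delay is m - 1.

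| z0 | d = 0.1 | d = 0.2 | d = 0.3 |
|---|---|---|---|
| -2.25 | m = 8 (-3.05), outside the 6 months | m = 4 (-3.05), delay 3 | m = 3 (-3.15), delay 2 |
| -2.5 | m = 6 (-3.1), delay 5 | m = 3 (-3.1), delay 2 | m = 2 (-3.1), delay 1 |
| -2.75 | m = 3 (-3.05), delay 2 | m = 2 (-3.15), delay 1 | m = 1 (-3.05), delay 0 |

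For z0 = -2.5 and d = 0.1, month 5 gives exactly -3.0, which is not below -3, hence month 6.

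**Step 3: limits of the illustration.** At each assumed rate the delay is an upper bound. The protocol also records MUAC and classifies children by weight-for-height, and either might count as severe sooner. The delay concerns the study's trigger; a Lady Health Worker or the family may act earlier.

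**The case against.** **This is an omission and not an error, and controls are meant to receive usual care.** The severe-malnutrition rule ignores group, and routine care continues. A reader might infer that control children are denied referral or left without care; the documents do not support that. What remains is that the study produces these weights itself, and what to do with them is a study procedure. The protocol already accepts study referral of controls at the severe threshold, so a referral does not breach the comparator in principle.

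**The asymmetry has a reason.** No gain after two weeks of supervised feeding and two of home support points more strongly to a medical cause than one flat month on usual feeding. This is fair, and a single flat interval may also reflect weighing error or brief illness. It argues for a repeat weighing before referral. It does not argue for no rule at all, least of all for a child who is losing weight.

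**The failure-to-thrive sentence already covers everyone.** It speaks of all children and gives the Hearth cycle only as an example. For treated graduates this largely stands: they belong to the arm under whose heading the sentence sits. A reader might infer that graduates have no safeguard before severe malnutrition; the text does not go that far, and a clarification is enough. For controls the reading is strained, because the sentence sits in the other arm's procedures and the protocol names both groups elsewhere when it means both.

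**The instruction may be in material not shown.** The consent forms (Section 9.2) and the survey and recruitment forms (Section 9.5) are cited but not at hand. If one of them carries the rule, a cross-reference suffices.

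**Conclusion.** The point holds for the control arm. As written, a control child with stalled or falling weight has no study referral until severe malnutrition, although the sponsor requires referral for a treated child with the same weight course over a cycle. For treated graduates the matter is one of wording only.

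This is a cheap safety improvement, not a flaw that undermines the trial. How many children it would affect cannot be derived from the protocol. The delays of 0 to 5 months, with one case not firing within follow-up, depend on the assumed Z-loss and on weight-for-age alone, and should not be read as forecasts. A reader might also infer that unequal referral biases the comparison of weight gain; nothing in the document allows the size of such an effect to be stated, and none is claimed.

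**What to change.** 1. In the control-arm procedures, under Anthropometric Assessment, add the treatment-arm rule at the monthly weighings already planned: no gain, or a loss, over about four weeks, confirmed by a repeat weighing, leads to referral to the public health facility within five days. Staff escort may stay specific to the treatment arm.
2. In the 28-day programme overview and the treatment-arm Health assessment text, state that the failure-to-thrive rule also applies to graduates at monthly check-ins.
3. Keep any note of referral (yes/no, date) as an operational safety record. The Health assessment text says that no health records beyond anthropometry are kept as study data, and the note should be worded to respect that.
4. Check the forms in Sections 9.2 and 9.5 and align them, or cross-refer if they already say this.

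Cost: a few sentences, a tick-box with a date, and some repeat weighings. There will be extra facility visits, of unknown number. If each takes as long as the baseline health assessment in Time to Participate, that is up to about 1 hour plus travel. The comparator becomes usual care plus a safety referral, which may slightly narrow the contrast between arms.
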